9.5 Side Effects

The known side effects of sildenafil include the following: *Prevalence > 10%:* Central nervous system: headache *Prevalence 1% to 10%:* Cardiovascular: flushing Central nervous system: dizziness Dermatologic: rash Genitourinary: urinary tract infection Ophthalmic: abnormal vision (color changes, blurred or increased sensitivity to light) Respiratory: nasal congestion *Prevalence < 2% (limited to important or life-threatening):*

Allergic reaction, angina pectoris, anorgasmia, asthma, AV block, cardiac arrest, cardiomyopathy, cataract, cerebral thrombosis, colitis, dyspnea, edema, exfoliative dermatitis, eye hemorrhage, gout, heart failure, hyperglycemia, hypotension, migraine, myocardial ischemia, neuralgia, photosensitivity, postural hypotension, priapism, rectal hemorrhage, seizure, shock, syncope, vertigo, tinnitus, transient or permanent unilateral or bilateral hearing loss.

In regards to potential toxicity, side effect prevalence was not dose dependent in the SUPER trial. Most adverse events were mild to moderate for all treatment groups and were not dose related as outlined above. Over 12 weeks, only two serious adverse events, postural hypotension and left ventricular dysfunction, were considered to be related to sildenafil. In contrast, in a large meta-analyses of 27 erectile dysfunction trials in 6659 men, studies which examined dose responsiveness did demonstrate a trend towards a dose response in the prevalence of side effects⁸⁵. However, the rate of discontinuation for side effects was lower in the active vs placebo arms. Side effects were not serious and the incidence of chest pain, myocardial infarction or death was not increased in premarketing or postmarketing studies. In this metaanalysis, there was no apparent increase in side effects according to baseline characteristics (age, diabetes, etc).

According to previous studies (summarized in package insert for sildenafil), healthy elderly volunteers (65 years or over) had a reduced clearance of sildenafil, with free plasma concentrations approximately 40% greater than those seen in healthy younger volunteers (18-45 years). Sildenafil is eliminated predominantly by hepatic metabolism and is converted to an active metabolite with biological properties (PDE-5 inhibition) similar to the parent, sildenafil. Sildenafil is cleared predominantly by the CYP3A4 (major route) and CYP2C9 (minor route) hepatic microsomal isoenzymes. The major circulating metabolite results from N-desmethylation of sildenafil, and is itself further metabolized. This metabolite has a PDE selectivity profile similar to sildenafil and an *in vitro* potency for PDE5 approximately 50% of the parent drug. Plasma concentrations of this metabolite are approximately 40% of those seen for sildenafil, so that the metabolite accounts for about 20% of sildenafil's pharmacologic effects. After either oral or intravenous administration, sildenafil is excreted as metabolites predominantly in the feces (approximately 80% of administered oral dose) and to a lesser extent in the urine (approximately 13% of the administered oral dose). In volunteers with mild (creatinine clearance = 50-80 mL/min) and moderate (creatinine clearance = 30-49 mL/min) renal impairment, the pharmacokinetics of a single oral dose of sildenafil (50 mg) were not altered. In volunteers with severe (creatinine clearance =<30 mL/min) renal impairment, sildenafil clearance was reduced, resulting in approximately doubling of AUC and Cmax compared to age-matched volunteers with no renal impairment. However, while these studies suggest reduced clearance of sildenafil in patients with renal dysfunction, a study in patients with end stage renal disease on hemodialysis showed that pharmacokinetics were similar to normal subjects both before and after hemodialysis⁸⁶.

Therefore, we initiate therapy with 20 mg tid recognizing the probable advanced age of study participants, up-titrate therapy at 12 weeks in the absence of side-effects, down titrate if increasing the dosage results in side effects but use a goal dose consistent with that providing the maximal hemodynamic effect in humans with PH and equivalent to that producing the observed myocardial effect in the mouse. Selection of this strategy provides the opportunity to maximize efficacy while minimizing side effects in this population.

At the study visits where the first dose of study drug (20 mg) is administered or the higher dose (60mg) is administered, systemic blood pressure measurement will be obtained in sitting and standing position one hour after administration of study drug. The dose of study drug will be stopped (therapy initiation visit) or reduced (therapy up-titration visit) in any patient in whom the SBP (seated or standing) measured 1 hour after the study drug during the drug initiation/titration visit is < 100 mm Hg or DBP < 40 mm Hg. Patients with chest pain, palpitations, diaphoresis will have a 12-lead ECG and a clinical evaluation as soon as possible. Study drug will be stopped in patients with acute coronary syndromes, AV block, or life-threatening arrhythmias.

At all study visits (in person or phone follow up), monitoring for toxicity will include questioning and encouragement to call the investigator about headache, flushing, dizziness, orthostatic lightheadedness, dyspepsia, nasal congestion, diarrhea, rash, visual disturbance, chest pain, palpitations, worsening dyspnea, peripheral edema, diaphoresis, tinnitus or hearing loss. On every study visit, investigators will obtain a medical history and perform a targeted cardiovascular physical examination. After each dose initiation or dose escalation, study coordinators will contact the patient by phone at 1 and 2 days after the dosing visit to monitor for adverse effects.

9.5.1 Potential for enhanced diuretic responsiveness:

Patients will be encouraged to weigh themselves daily and patients will undergo measurement of weight at each study visit on the same scale. In patients complaining of lightheadedness, dizziness or other symptoms of low blood pressure or with decreases in blood pressure on measurement, the study staff will determine if evidence of increased diuretic responsiveness is present (decrease in weight on same diuretic dose and without increased signs of volume overload on examination). If evidence of enhanced diuretic responsiveness is present, consideration will be given to reducing diuretic dose before adjusting study drug dosage.

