8.3 Exclusion Criteria

- 1. Have a neuromuscular, orthopedic or other non-cardiac condition that prevents patient from exercise testing on a bicycle ergometer or from walking in a hallway
- 2. Non-cardiac condition limiting life expectancy to less than one year, per physician judgment
- 3. Current or anticipated future need for nitrate therapy
- 4. Valve disease (> mild aortic or mitral stenosis; > moderate aortic or mitral regurgitation)
- 5. Hypertrophic cardiomyopathy
- 6. Infiltrative or inflammatory myocardial disease (amyloid, sarcoid)
- 7. Pericardial disease
- 8. Primary pulmonary arteriopathy
- Have experienced a myocardial infarction or unstable angina, or have undergone percutaneous transluminal coronary angiography (PTCA) or coronary artery bypass grafting (CABG) within 60 days prior to consent, or requires either PTCA or CABG at the time of consent
- 10. Other clinically important causes of dyspnea such as morbid obesity or significant lung disease defined by clinical judgment or use of steroids or oxygen for lung disease
- 11. Systolic blood pressure < 110 mmHg or > 180 mm Hg
- 12. Diastolic blood pressure < 40 mmHg or > 100 mmHg
- 13. Resting heart rate (HR) > 100 bpm
- 14. A history of reduced ejection fraction (EF<50%)
- 15. Implanted metallic device which will interfere with MRI examination (in patients without atrial fibrillation)
- 16. Severe renal dysfunction (estimated GFR < 20 ml/min/1.73m² by modified MDRD equation) GFR (mL/min/1.73 m²) = 175 x (S_{cr})^{-1.154} x (Age)^{-0.203} x (0.742 if female) x (1.210 if African American) (conventional units)
- 17. Women of child bearing potential who do not have a negative pregnancy test at study entry and who are not using effective contraception
- 18. Hemoglobin <10 g/dL
- 19. Patients taking alpha antagonists or cytochrome P450 3A4 inhibitors (ketoconazole, itraconazole, erythromycin, saquinavir, cimetidine or serum protease inhibitors for HIV).
- 20. Patients with retinitis pigmentosa, previous diagnosis of nonischemic optic neuropathy, untreated proliferative retinopathy or unexplained visual disturbance
- 21. Patients with sickle cell anemia, multiple myeloma, leukemia or penile deformities placing them at risk for priapism (angulation, cavernosal fibrosis or Peyronie's disease)
- 22. Patients with severe liver disease (AST > 3x normal, alkaline phosphatase or bilirubin > 2x normal)

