9. TREATMENT INTERVENTIONS

9.1 Intervention

The therapeutic intervention is double blinded therapy with placebo or the PDE-5 inhibitor sildenafil (as Revatio[®]). Study drug therapy will be given for 24 weeks starting with 20 mg by mouth three times a day (tid) for 12 weeks. If that dose is well tolerated, the dose will be increased to 60 mg tid at week 12 for the remaining 12 weeks of the study. Patients unable to tolerate the 60 mg tid will be maintained on the 20 mg tid dose. The active and placebo study medication will appear identical to preserve the double blind design of the study. If patients develop side effects thought potentially related to study drug (including but not limited to headache, flushing, dizziness, orthostatic lightheadedness, dyspepsia, nasal congestion, diarrhea, rash, visual disturbance), the dose will be adjusted to the previously tolerated dose. As recommended for patients with HF, patients will be encouraged to weigh daily and record weights. If patients have experienced enhanced responsiveness to their diuretic dosage (decreased weight *and* symptoms of over-diuresis such as lightheadedness), consideration can be given to reducing the diuretic dose rather than the study drug.

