The concomitant use of potent cytochrome P450 3A4 inhibitors (e.g., erythromycin, ketoconazole, itraconazole) as well as the nonspecific CYP inhibitor, cimetidine, is associated with increased plasma levels of sildenafil. Patients taking these drugs are excluded from this protocol and patients enrolled in the study will be cautioned not to commence therapy with these agents. Patients enrolled in the trial will receive a card outlining potential drug interactions and be instructed to present this card if new medications are recommended during the trial. This wallet card will also contain the DCC Clinical Helpline number for emergent unblinding and for reporting of side effects. Patients will also be given a medic alert necklace indicating the patient may be taking sildenafil. Clearance is also reduced in patients > 65 and in those with severe renal or severe hepatic dysfunction where an initial dose of 20 mg is recommended. Patients with significant liver disease (AST>3x normal or alkaline phosphatase or bilirubin > 2x normal) are excluded from this protocol. Side effects reported to occur in $\geq 2\%$ of patients in phase II/III clinical trials of Sildenafil have included headache (16%), flushing (10%), dyspepsia (7%), nasal congestion (4%), urinary tract infection (3%), abnormal vision (3%), and diarrhea, dizziness and rash (2% each). Transient visual changes can occur with sildenafil due to effects on PDE-6 in the eye. Sildenafil is guite specific for PDE-5 but some cross-reactivity can occur at higher doses and produce transient color distortion, halo-vision, or blurred vision. Ocular effects from PDE-5 inhibition include conjunctival hyperemia. However, extensive testing in PH patients and in erectile dysfunction patients treated with sildenafil has not revealed any permanent effects on visual acuity, visual fields, color sensitivity or fundoscopic examination associated with chronic daily or intermittent sildenafil dosing, even at doses of 50-100 mg (data on file, Pfizer).

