13. FOLLOW-UP EVALUATIONS

13.1 Evaluations Performed During the Follow-up Period

The following studies will be performed during the follow up period after starting study drug. Please see section 14 for a detailed description of these procedures section 22 (Appendix 22.1) for the schedule of evaluations.

Week -4 to 0: Consent, Screening studies and Baseline studies

Week 0: Randomization and initial dosing visit (Study Coordinator) (Phone follow up x 2 days)

Week 1: Phone contact to assess study drug tolerance (Study Coordinator)

Week 3: Study visit and evaluations (Study Coordinator)

- 1. Creatinine
- 2. History
- 3. Limited physical examination including bedside hearing assessment

Week 8: Phone contact to assess study drug tolerance (Study Coordinator)

- Week 12: Study visit and evaluations and dose escalation (Study coordinator and PI) 1. History
 - 1. History
 - 2. Physical examination including bedside hearing assessment
 - 3. Metabolic stress test with sildenafil level immediately prior to the study.
 - 4. Six minute walk test
 - 5. Minnesota Living with Heart Failure Questionnaire
 - 6. Creatinine
 - 7. Dose escalation (60 mg tid) (Phone follow up x 2 days)
- Week 13: Phone contact to assess study drug tolerance (Study Coordinator)
- Week 16: Phone contact to assess study drug tolerance (Study Coordinator)
- Week 20: Phone contact to assess study drug tolerance (Study Coordinator)

Week 24: Final study visit and evaluations (Study coordinator and PI)

- 1. Limited Doppler echocardiography
- 2. Cardiac Magnetic Resonance Imaging (MRI) (Patients in sinus rhythm only)
- 3. Phlebotomy for Biomarkers
- 4. Metabolic stress test with sildenafil level immediately prior to the study.
- 5. Six minute walk test
- 6. Minnesota Living with Heart Failure Questionnaire
- 7. Creatinine
- 8. Clinical history
- 9. Physical examination including bedside hearing assessment

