100 mg	1	Normal (?)	PO	450	1	1 h after dose
50 mg	1	SHF (13)	PO	237 ± 23	4	1 h after dose
40 mg tid	18	Normal at high altitude (6)	PO	254	5	1-2 h after dose
25 mg tid	Chronic	SHF (7)	PO	78 ± 23	6	Random level
50 mg tid	Chronic	SHF (4)	PO	88 ±12	6	Random level
75 mg tid	Chronic	SHF (4)	PO	220 ± 84	6	Random level

Table 1. Published data on plasma sildenafil levels following acute and chronic administration to humans.

SHF = systolic heart failure

Sildenafil is hepatically metabolized; in volunteers with mild (Ccre = 50-80 ml/min) and moderate (Ccre = 30-49 ml/min) renal impairment, the pharmacokinetics of a single oral dose of sildenafil (50 mg) are not altered. Plasma levels increase in patients with severe renal impairment (Ccre < 30 ml/min)(1).

The principle metabolite (UK 103320) of sildenafil circulates at about 40% of sildenafil concentration and has 50% of sildenafil's binding affinity to PDE5 (1). Thus UK 103320 contributes an additional 20% to PDE5 inhibition at a given level of circulating sildenafil, as it is not measured in the sildenafil plasma assay.

Summary: The peak plasma sildenafil concentration drawn –2 hours after administration of 40-50 mg is ~260 ng/ml (390 nM*). The plasma half-life after peak level is achieved is 3.2-4 hours. When administered every 8 hours, the trough is only 18% of the peak concentration. Thus, the peak level one to two hours after a dose during chronic administration is similar to that seen with single dose. That randomly drawn plasma levels intervals of sildenafil exhibit large variation is explained by the wide peak-to-trough ratio seen in tid dosing (6).

2. Relationship of Dose to Response

Several studies examining the relationship of sildenafil level to the biologic response have been performed. These include studies of vascular smooth muscle relaxation ex vivo, studies of animal models of pulmonary vasoconstriction, and clinical studies in patients with PAH and with left ventricular systolic dysfunction.

2A: Ex vivo studies of vascular tissue. Human coronary, internal mammary, and radial arteries were obtained from deceased organ donors, pre-constricted with the prostacyclin analogue U-46619, and exposed to sildenafil in modified Krebs solution (7). Rat aorta was harvested and preconstricted with phenylephrine prior to exposure to sildenafil (8). The concentration of sildenafil yielding half-maximal vasodilation and the range of concentrations yielding 10-90% vasodilation are given in Table 2.

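### Patients with eGFR 20-30 step to 60 mg tid at week 12 with no renal condition, although Section 9.5 reports about doubled exposure in severe renal impairment

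*Protocol*

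**What the plan says.** **Eligibility.** Section 8.3, item 16, excludes "Severe renal dysfunction (estimated GFR < 20" mL/min/1.73 m², by the modified MDRD equation). Patients between 20 and 30 are therefore eligible.

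**Dosing.** All patients start on 20 mg tid. Section 9.1 then states: "If that dose is well tolerated, the dose will be increased to 60 mg tid at week 12". It also provides a fallback: "Patients unable to tolerate the 60 mg tid will be maintained on the 20 mg tid dose". The week-12 list in Section 13.1 has creatinine, a sildenafil level and "Dose escalation (60 mg tid) (Phone follow up x 2 days"). Nothing links either laboratory result to the step. Section 9.5 adds a seated and standing blood pressure one hour after the first 60 mg dose, with a dose reduction if systolic pressure is below 100 or diastolic below 40 mm Hg.

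**Renal pharmacokinetics.** Section 9.5 says that mild and moderate impairment (clearance 30-80 mL/min) left a single 50 mg dose unaffected, but that at 30 mL/min or less "sildenafil clearance was reduced, resulting in approximately doubling of AUC and Cmax compared to age-matched volunteers with no renal impairment". The next sentence cites a hemodialysis study with pharmacokinetics similar to normal. Appendix 3 repeats that exposure rises in severe impairment: "Plasma levels increase in patients with severe renal impairment (Ccre < 30 ml/min").

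**Renal dosing.** The only statement is in 9.6.3, which says that clearance is reduced "in those with severe renal or severe hepatic dysfunction where an initial dose of 20 mg is recommended". Every patient in the trial gets that starting dose. The rationale that follows the renal data in 9.5 reads "Therefore, we initiate therapy with 20 mg tid recognizing the probable advanced age of study participants, up-titrate therapy at 12 weeks". It names age and not renal function.

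**The concern.** The protocol treats raised sildenafil levels as a hazard in other settings. It excludes patients on CYP3A4 inhibitors or cimetidine, and patients with significant liver disease. The renal group for which it reports about doubled exposure gets a threefold dose step on the same terms as everyone else.

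The blood pressure check can reverse the step but does not guard it, and it reflects one dose rather than sustained tid dosing. Section 17.2.2 lists worsening renal function among the study-drug-related events. A patient who enters above eGFR 30 and falls below it by week 12 would therefore also be escalated under the written rule, with the creatinine in hand.

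What is at stake is the safety of a small group. The primary analysis, error rate and power are not involved.

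**Working it through.** **1. The plan's own dose figure.** Section 9.4 gives 0.66-2.57 mg/kg/day for 70-90 kg. Check: 3 × 20 / 90 = 0.67 and 3 × 60 / 70 = 2.57. It reproduces, but it is a nominal dose with no allowance for reduced clearance.

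**2. Exposure-equivalent dose.** Inputs: doses of 20 and 60 mg tid (9.1); exposure ratio R of about 2 at clearance of 30 mL/min or less, or about 1 if the hemodialysis result carries over (both 9.5); upper end of the Appendix 3 concluding range, 80 mg tid. Assumption: exposure is proportional to dose, so equivalent dose = dose × R.

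| R | 20 mg tid acts like | 60 mg tid acts like | 60 mg tid against 80 mg tid |
|---|---|---|---|
| 1.0 | 20 | 60 | inside |
| 1.33 | 26.7 | 80 | at the limit |
| 1.5 | 30 | 90 | above |
| 2.0 | 40 | 120 | above, 120/80 = 1.5 |

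Break-even ratios are 80/60 = 1.33 for 60 mg tid and 80/20 = 4 for 20 mg tid.

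**3. Against the other doses cited.** Doubled 60 mg tid is 3 × 60 × 2 = 360 mg/day, and 80 mg tid is 240 mg/day. Section 9.6.3 mentions pulmonary hypertension patients given up to 200 mg bid, which is 400 mg/day. So 360 is above the Appendix 3 range but below the highest adult daily dose mentioned.

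**4. Can Appendix 3, Table 1, replace the proportionality assumption?** Take exposure ∝ dose^b, with b = ln(level ratio) / ln(dose ratio).

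- 50 to 100 mg, one hour after a single dose: ln(450/265)/ln 2 = 0.76, or ln(450/237)/ln 2 = 0.93
- 25 to 75 mg tid, random levels: ln(220/78)/ln 3 = 0.94
- 25 to 50 mg tid, random levels: ln(88/78)/ln 2 = 0.17
- 50 to 75 mg tid, random levels: ln(220/88)/ln 1.5 = 2.26

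Doubled exposure at 60 mg tid, relative to 80 mg tid without impairment, is 2 × (60/80)^b. It is 1.90 at b = 0.17 and 1.04 at b = 2.26. The direction holds across that span, but the size is not pinned down. The chronic groups have 4 to 7 patients each, and the table also lists a 610 ng/ml maximum after 50 mg against 450 after 100 mg.

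The same formula for 20 mg tid, 2 × (20/80)^b, stays at or below 1 only if b is at least 0.5. At b = 0.17 it would be about 1.6, so the protection from holding at 20 mg also assumes that exposure rises reasonably with dose.

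**5. How many patients.** The protocol does not say. At an assumed 0-10% of 215 there would be 0 to 21.5 patients, about half of them (0 to 10.8) on sildenafil.

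**6. Matching eGFR to clearance.** Exclusion 16 is indexed to 1.73 m² and 9.5 is in mL/min. At an assumed body surface of 1.6-2.2 m², eGFR 30 corresponds to 30 × 1.6/1.73 = 27.7 up to 30 × 2.2/1.73 = 38.2 mL/min. The two thresholds agree only roughly.

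**The case against.** The strongest reply is that this was a considered choice on mixed evidence. Section 9.5 sets out the renal doubling, qualifies it with the hemodialysis study, notes mainly hepatic elimination (about 13% of an oral dose in urine), and then describes a low start with symptom-guided titration. If exposure doubles, these patients will already have tolerated the equivalent of about 40 mg tid for 12 weeks. Entry systolic pressure must be at least 110. Pressure is checked about when levels peak, and calls follow on days 1 and 2 and in weeks 13, 16 and 20. Section 9.5 also describes side effects in the pulmonary arterial hypertension dose-ranging trial as not dose dependent.

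Much of this stands. The safeguards are real, and the affected group could be empty. But the hemodialysis patients had end-stage disease, which exclusion 16 largely keeps out, whereas the group with doubled exposure overlaps the eligible band. Section 9.6.3 and Appendix 3 restate reduced clearance or raised levels without the qualification. The side-effect evidence is not uniform either: Appendix 3 reports a trend to more vasodilatory effects with dose, and 9.5 a similar trend in the erectile dysfunction trials.

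A reader might infer that these patients would exceed every dose with human experience behind it. The documents do not support that. Section 9.6.3 cites up to 400 mg/day, although without tolerability or renal results for those patients, and Appendix 3 sets no formal ceiling. A reader might also take a tight multiple such as 1.5-1.6 from Table 1. That rests on three of its possible pairs, and others in the same table give 1.04 to 1.90.

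**Conclusion.** The point holds as a conditional safety gap. Patients with eGFR 20-30 are eligible, the protocol itself reports about doubled AUC and Cmax at clearance of 30 mL/min or less, and the week-12 step has no renal condition. If the doubling applies and exposure is roughly dose-proportional, 60 mg tid acts like about 120 mg tid. That exceeds the 20-80 mg tid range that Appendix 3 concludes appears safe for chronic use, while 20 mg tid acts like about 40 mg tid and stays inside it. If the hemodialysis result applies instead, nothing is exceeded. The documents do not show that these patients would be harmed. The conclusion rests on the exposure ratio, on rough dose-proportionality and on an approximate match between eGFR and clearance. The number of patients is unknown and probably small. This is a cheap improvement worth making, and it does not threaten the trial's validity.

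**What to change.** Add to Sections 9.1 and 13.1, identically in both blinded arms:

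*Patients whose most recent study eGFR at the week-12 visit is below 30 stay on 20 mg tid. If the week-12 creatinine reported after the visit gives eGFR below 30, return to 20 mg tid at the next scheduled phone contact.*

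This uses creatinine already drawn at weeks 3 and 12, the fallback dose already in 9.1, and the calls already planned for days 1 and 2 and week 13. No visit or blood draw is added. It does not rely on later clinical creatinines, because no study creatinine is scheduled between weeks 12 and 24.

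**Cost.** A few patients per arm would not reach the goal dose. Some would be large patients whose clearance is above 30: at an assumed 2.2 m², a clearance of 30 mL/min is eGFR 30 × 1.73/2.2 = 23.6, so those between 23.6 and 30 would be held although 9.5 reports unaltered pharmacokinetics there. A late result means reversing a dose already dispensed. The pre-specified subgroup by dose of sildenafil achieved (18.7) would become somewhat more tied to renal function. Eligibility, sample size, endpoints and error rate do not change.
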